Objectives	
Primary Objective
 
The primary objective is to determine the objective response rate (ORR) of treatment with milademetan in patients with advanced/metastatic solid tumors with murine double minute 2 (MDM2) gene amplification.
 
Secondary Objectives
 
• To assess treatment with milademetan for the following efficacy parameters:
◦ Duration of response (DOR)◦ Progression-free survival (PFS)◦ Growth modulation index (GMI)◦ Disease control rate (DCR)◦ Overall survival (OS)• To assess the safety profile of milademetan• To evaluate patient-reported health-related quality of life with the European Organisation for Research and Treatment of Cancer Quality-of Life Questionnaire, Core 30 (QLQ-C30) 
Exploratory Objectives
  
-1)

Study Design	
This is a Phase 2, multicenter, single-arm, open-label basket study designed to evaluate the safety and efficacy of milademetan in patients with advanced or metastatic solid tumors refractory or intolerant to standard-of-care therapy that exhibit wild-type (WT) tumor protein 53 (TP53) gene and MDM2 copy number (CN) ≥ 8 using prespecified biomarker criteria.
 
Approximately 65 patients will be enrolled to receive milademetan.
 
Patients will receive the study drug until reaching unequivocal disease progression (per Response Evaluation Criteria in Solid Tumors [RECIST] version [v]1.1), as determined by the Investigator; experiencing unmanageable toxicity; or until other treatment discontinuation criteria are met. Patients may be treated beyond tumor progression if

	
they are experiencing clinical benefit based on the assessment of the Investigator in discussion with the Sponsor's Medical Monitor.
 
All patients will be followed for documentation of disease progression and survival information (i.e., date and cause of death). Long-term follow-up will continue every 12 weeks (\pm 7 days) until the endpoint of death, the patient is lost to follow-up, or for 24 months after the first dose of study drug for the last patient, whichever comes first.

Investigational Treatment (Milademetan)	
Dose and Mode of Administration: 260 mg administered orally once daily (QD) on Days 1 to 3 and Days 15 to 17 of each 28-day cycle.
 
Eligibility	
Inclusion Criteria
 
Each patient must meet all of the following criteria to be enrolled in the study:
 
1. Is a patient \geq 18 years old2. Has signed and dated an informed consent form prior to the start of any study-specific qualification procedures3. Has histologically and/or cytologically confirmed diagnosis of a cancer that is a locally advanced or metastatic solid tumor4. Has measurable tumor lesion(s) in accordance with RECIST v1.15. Must have received all standard therapy appropriate for their tumor type and stage of disease or, in the opinion of the Investigator, would be unlikely to tolerate or derive clinically meaningful benefit from appropriate standard-of-care therapy 

	
6. Has resolution of any clinically relevant toxic effects of prior chemotherapy, surgery, radiotherapy, or hormonal therapy
 
	
8. Has an Eastern Cooperative Oncology Group (ECOG) performance status of 0 or 1
 
9. Has adequate bone marrow function, defined as:
 
a. Platelet count $\geq 100 \times 10^9/L$b. Hemoglobin $\geq 9.0 \text{ g/dL}$c. Absolute neutrophil count $\geq 1.5 \times 10^9/L$ 
10. Has adequate renal function, defined as creatinine clearance $\geq 30 \text{ mL/min}$, as calculated using the modified Cockcroft-Gault equation (or equivalent glomerular filtration rate calculated using the Chronic Kidney Disease Epidemiology Collaboration formula)
 
11. Has adequate hepatic function, defined as:

	
a. Alanine aminotransferase and aspartate aminotransferase $\leq 3 \times$ the upper limit of normal (ULN) if no liver metastases are present or $\leq 5 \times$ ULN if liver metastases are presentb. Total bilirubin $\leq 1.5 \times$ ULN or $\leq 3 \times$ ULN in the presence of liver metastases. Patients with Gilbert's disease who have serum bilirubin levels $> 3 \times$ ULN may be enrolled12. Is willing and able to comply with the protocol requirements13. If requiring anticoagulation medication, should be on a stable regimen, defined as being on the same dose for at least 4 weeks14. If a woman of childbearing potential (WOCBP), they must have a negative serum pregnancy test at Screening and a negative urine pregnancy test on Cycle 1 Day 1 before receiving the first dose of study drug or within 72 hours of the first dose of study drug

15. If a male patient, is surgically sterile, willing to use a condom, or remain abstinent upon enrollment through the Treatment Period and until at least 90 days after the final dose of the study drug

--	--

Exclusion Criteria

A patient who meets any of the following criteria will not be eligible to participate in the study:

[figure not shown]
1. Has had prior treatment with an MDM2 inhibitor
2. Has well-differentiated/dedifferentiated liposarcoma or intimal sarcoma/cardiac sarcoma
3. Has other primary malignancies that required systemic antineoplastic treatment within the previous 2 years, except for localized cancers that have apparently been cured (e.g., nonmelanoma skin cancer, superficial bladder cancer, or carcinoma in situ of the cervix or breast) and will not interfere with the study outcomes
4. Has a primary malignant brain tumor of any grade or histology
5. Has untreated brain metastases

[figure not shown]
	
6. Has gastrointestinal conditions that could affect the absorption of milademetan, in the opinion of the Investigator
 
[REDACTED]
 
7. Has a clinically significant uncontrolled infection within the last 7 days requiring intravenous antibiotics, antivirals, or antifungals
 
8. Has known HIV infection or active hepatitis B or C infection
 
9. Has not met the minimum washout period before enrollment, defined as:
 
a. Cytochrome P450 (CYP)3A4 isozyme strong inhibitor: 5 elimination half-lives of the inhibitorb. CYP3A4 strong or moderate inducers (e.g., St. John's wort and modafinil): 4 weeksc. Systemic anticancer therapy (chemotherapy; small molecules, including antibody drug therapy; retinoid therapy; or hormonal therapy) or investigational therapy: 3 weeks or 5 half-lives, whichever is shorterd. Immunotherapy with a checkpoint inhibitor: 4 weeks 
10. Has had major surgery \leq 3 weeks from Cycle 1 Day 1
 
11. Has had curative-intent radiation therapy \leq 4 weeks or palliative radiation therapy, defined as \leq 30 Gy in \leq 10 fractions (e.g., 20 Gy in 5 fractions or 8 Gy in 1 fraction), \leq 2 weeks from Cycle 1 Day 1
 
12. Has uncontrolled or significant cardiovascular disease, including:
 
a. Corrected QTc interval as calculated according to Fridericia's formula (QTcF) at rest, where the mean QTcF interval is $>$ 480 ms (average of triplicate 12-lead electrocardiograms [ECGs]) in the absence of an offending medication that can be safely discontinuedb. Myocardial infarction within 6 months prior to Screeningc. Uncontrolled angina pectoris within 6 months prior to Screeningd. New York Heart Association Class 3 or 4 congestive heart failuree. Uncontrolled hypertension (resting systolic blood pressure $>$ 150 mm Hg or diastolic blood pressure $>$ 100 mm Hg) on repeat measurements and despite adequate medical management 
13. Is a woman who is pregnant or breastfeeding or intends to become pregnant during the study
 
14. Has a concomitant medical condition that would interfere with the assessment of efficacy or increase the risk of toxicity, in the opinion of the Investigator or Sponsor

Criteria for Efficacy Evaluation	The primary efficacy endpoint is ORR, and the secondary efficacy endpoints are DOR, PFS, GMI, DCR, and OS. Health-related quality-of-life evaluations include the QLQ-C30.

	
The ORR is defined as the percentage of patients who have achieved a confirmed complete response (CR) or partial response (PR).
 
Tumor assessments via imaging (computed tomography scans or magnetic resonance imaging) will be performed by the Investigator; the evaluation of tumor response will be based on RECIST v1.1.
 
Tumor response evaluations will be performed at Screening and then every 8 weeks (± 7 days) while the patient remains on the study drug, and any other time during the study as clinically indicated. In accordance with RECIST version 1.1, response (PR and CR) must be confirmed by a subsequent tumor assessment at least 4 weeks after the initial observed response.
 
The secondary efficacy endpoints DOR, PFS, GMI, DCR, and OS are defined as:
 
• The DOR is defined as the time from the date of first response to the date of disease progression or death• The PFS is defined as the time from the date of first dose to the earliest date of the first objective documentation of radiographic disease progression or death due to any cause• The GMI will be determined using the ratio of time to progression (TTP) with nth line of therapy (TTP_n; here defined as milademetan) to the most recent prior line of therapy (TTP_{n-1})• The DCR is defined as the percentage of patients who have achieved confirmed CR, PR, or stable disease (SD) lasting for ≥ 16 weeks• OS, as measured from the date of the first dose of the study drug to the date of death due to any cause 
Health-related quality-of-life endpoints include QLQ-C30.

Criteria for Safety Evaluation	Safety endpoints include the incidence of treatment-emergent AEs (TEAEs); including serious AEs, TEAEs leading to dose reductions, TEAEs leading to discontinuation of the study drug, and TEAEs leading to study withdrawal; changes in clinical laboratory parameters (hematology, serum or plasma chemistry, and urine pregnancy test), deaths, vital signs, and ECG parameters (especially QT intervals); physical examination results; and use of concomitant medications.
Criteria for Pharmacokinetic Evaluation	
Exploratory Evaluations	

Statistical Methods	

[figure not shown]

TABLE OF CONTENTS

STATEMENT OF THE SPONSOR.....	2
PROTOCOL VERSION HISTORY	3
SYNOPSIS5	
TABLE OF CONTENTS.....	16
LIST OF TABLES.....	19
LIST OF FIGURES	20
LIST OF ABBREVIATIONS.....	21
1. INTRODUCTION	24
2. BACKGROUND INFORMATION	25
2.1. Milademetan	25

MRI	magnetic resonance imaging
NCI	National Cancer Institute
NOAEL	no-observed-adverse-effect level
ORR	objective response rate
OS	overall survival
p21	cyclin-dependent kinase inhibitor 1
p53	Tumor suppressor protein 53
P-gp	P-glycoprotein
PD	progressive disease
PDX	patient-derived xenograft
PFS	progression-free survival
PK	pharmacokinetic(s)
PR	partial response
PUMA	p53 upregulated modulator of apoptosis
QD	once daily
QLQ-C30	European Organisation for Research and Treatment of Cancer Quality-of-Life Questionnaire, Core 30
QTc	corrected QT interval
QTcF	corrected QTc interval as calculated according to Fridericia's formula
RECIST	Response Evaluation Criteria in Solid Tumors
SAE	serious adverse event
SAP	statistical analysis plan
SD	stable disease
SJSA-1	osteosarcoma cell line
TEAE	treatment-emergent adverse event
TP53	tumor protein p53 gene
TTT	time to progression
TTT _n	time to progression with the nth line of therapy
TTT _{n-1}	time to progression to the most recent prior line of therapy
ULN	upper limit of normal
US	United States
v	version
WHO	World Health Organization
WOCBP	women of childbearing potential
WT	wild type

1. INTRODUCTION

The tumor suppressor protein p53 plays an essential role in preventing neoplasia by inducing cell cycle arrest or apoptosis in cells undergoing various types of physiological stress. However, inactivation of TP53 by mutation occurs in a significant percentage of human tumors, resulting in a loss of tumor suppressor activity and thereby removing a pivotal barrier to neoplastic development. In human tumors that retain WT p53 protein, its activity is frequently inhibited by intermolecular interactions between p53 and MDM2. MDM2 and p53 form a regulatory feedback loop in which MDM2 maintains low levels of p53 activity in normal, unstressed cells by promoting export of p53 out of the nucleus and proteasome-mediated degradation of p53 through its E3 ubiquitination ligase activity ([Shangary 2009](#)). In the presence of stress, p53 becomes activated and subsequently acts as a transcription factor that modulates the expression of a variety of genes, including MDM2 ([Levine 2009](#)). The MDM2 binding domain on p53 overlaps with the transcriptional activation domain of p53, thereby inhibiting the activity of p53. Thus, in human tumors, disruption of MDM2/p53 balance through overexpression and/or oncogenic activation of MDM2 allows tumorigenesis and tumor growth by preventing p53 function.

In patients with cancers that do not harbor TP53 mutations, MDM2 gene amplification or increased MDM2 activity represent an alternate path for loss of p53 function. Alterations, such as gene amplification, are associated with tumorigenic potential ([Fakharzadeh 1991](#)) and thus, may serve as a predictive biomarker of antitumor activity with MDM2 inhibitors. MDM2 gene amplification is found across solid tumors at varying frequencies and with varying levels of gene amplification. Pharmacologic inhibition of the interaction between MDM2 and WT p53 in tumor cells could result in sustained increases in p53 activity and subsequent antitumor effects ([Vassilev 2004](#), [Shangary 2008](#)). Therefore, pharmacologic restoration of the p53 pathway could be an effective strategy for cancer therapy targeting the wide array of human cancers that retain WT p53 ([Vassilev 2007](#)).

[figure not shown]
Milademetan (RAIN-32) is a small-molecule inhibitor of MDM2 that disrupts the interactions between MDM2 and the tumor suppressor protein p53 ([Noguchi 2019](#)). MDM2 expression and/or activity can be upregulated by multiple mechanisms in cancer cells including *MDM2* gene amplification ([Tirunagaru 2021](#)), cyclin-dependent kinase inhibitor 2A gene (*CDKN2A*) loss ([Sherr 2000](#)), and Merkel cell polyomavirus-encoded small T antigen ([Park 2021](#)) among other mechanisms, leading to potential MDM2-dependency and sensitivity to milademetan.

This is a Phase 2 multicenter, single-arm, open-label basket study designed to evaluate the safety and efficacy of milademetan in patients with advanced or metastatic solid tumors refractory or intolerant to standard-of-care therapy and that exhibit WT *TP53* and *MDM2* CN ≥ 8 using prespecified biomarker criteria. The primary objective of the study is to determine the ORR of treatment with milademetan in these patients.

[figure not shown]
2. BACKGROUND INFORMATION

[figure not shown]
2.1. Milademetan

[figure not shown]
Milademetan is a novel, specific, small-molecule inhibitor of MDM2 that disrupts the interactions between MDM2 and the tumor suppressor protein p53 in tumor cells, preventing excessive degradation of p53 (Noguchi 2019). In normal cells, the balance of MDM2 and p53 levels are maintained by a feedback mechanism in which p53 induces MDM2 expression, and the MDM2-p53 interaction promotes nuclear export of p53 and its proteasome-mediated degradation through the E3 ubiquitin ligase activity of MDM2 (Vassilev 2004). Mutational inactivation of p53 occurs in a significant percentage of human tumors, resulting in the loss of tumor suppressor activity in tumor cells. In human tumors that harbor WT *TP53*, MDM2 levels or activity are frequently elevated by *MDM2* gene amplification or other mechanisms of overexpression, resulting in increased MDM2-p53 interaction and loss of p53 tumor suppressor function due to its degradation. Pharmacologic disruption of the interaction between MDM2 and p53 by milademetan in animal models of tumors that harbor WT *TP53* have demonstrated sustained increases in p53 activity with a resultant antitumor effect (Vassilev 2007).

[figure not shown]

2.1.1.1. In Vitro Pharmacology Studies

[figure not shown]

[figure not shown]

[figure not shown]

[figure not shown]

2.4. Rationale for Dose Selection

2.5. Benefit/Risk Assessment

Current evidence supports the continued study of milademetan in clinical studies.

Preclinical and preliminary clinical data support the development of milademetan in patients with advanced or metastatic solid tumors that are refractory or intolerant to standard-of-care therapy and exhibit WT *TP53* and *MDM2* CN ≥ 8 . The mechanism of action of milademetan, the inhibition of MDM2 which increases p53 activity with a resultant antitumor effect, suggests a potential benefit in this patient population.

Overall, milademetan was generally well tolerated, with an acceptable benefit/risk assessment.

3. STUDY OBJECTIVES AND PURPOSE

The purpose of the study is to evaluate the safety and efficacy of milademetan in patients with advanced/metastatic solid tumors with WT *TP53* and *MDM2* gene amplification. To be eligible, patients must have progressed on 1 or more prior systemic therapies.

[figure not shown]
3.1. Primary Objective

The primary objective of the study is to determine the ORR of treatment with milademetan in patients with advanced/metastatic solid tumors with *MDM2* gene amplification.

3.2. Secondary Objectives

The secondary objectives of the study are:

- To assess treatment with milademetan for the following efficacy parameters:
 - DOR
 - PFS
 - GMI
 - DCR
 - OS
- To assess the safety profile of milademetan
- To evaluate patient-reported quality-of-life questionnaire (QLQ-C30)

4. STUDY DESIGN

4.1. Study Design Overview

This is a Phase 2, multicenter, single-arm, open-label basket study designed to evaluate the safety and efficacy of milademetan in patients with advanced or metastatic solid tumors refractory or intolerant to standard-of-care therapy that exhibit WT *TP53* and *MDM2* CN ≥ 8 using prespecified biomarker criteria. Local lab results for determination of *TP53* mutation status

and *MDM2* amplification may be used for eligibility; verification of *MDM2* CN should be performed using a central laboratory as outlined under Section 5.1 Inclusion Criteria.

Approximately 65 patients will be enrolled to receive milademetan.

Patients will receive the study drug until reaching unequivocal disease progression (per RECIST v1.1), as determined by the Investigator; experiencing unmanageable toxicity; or until other treatment discontinuation criteria are met. Patients may be treated beyond tumor progression if patients are experiencing clinical benefit based on the assessment of the Investigator in discussion with the Sponsor's Medical Monitor.

All patients will be followed for documentation of disease progression and survival information (i.e., date and cause of death). Long-term follow-up (LTFU) will continue every 12 weeks (\pm 7 days) until the endpoint of death, the patient is lost to follow-up, or for 24 months after the first dose of the study drug for the last patient, whichever comes first.

4.2. Endpoints and Criteria for Evaluation

4.2.1. Primary Endpoint

The primary efficacy endpoint is ORR. The ORR is defined as the percentage of patients who have achieved a confirmed CR or PR. Tumor response will be assessed in accordance with RECIST v1.1.

[figure not shown]
4.2.2. Secondary Endpoints

Secondary efficacy endpoints include:

- The DOR, defined as the time from the date of first response to the date of disease progression or death
- The PFS, defined as the time from the date of first dose to the earliest date of the first objective documentation of radiographic disease progression or death due to any cause
- The GMI will be determined using the ratio of TTP with TTP_n (here defined as milademetan) to TTP_{n-1}
- The DCR, defined as the percentage of patients who have achieved confirmed CR, PR, or SD for ≥ 16 weeks
- OS, as measured from the date of the first dose of the study drug to the date of death due to any cause

Health-related quality-of-life endpoints include the QLQ-C30.

Safety endpoints include the incidence of TEAEs (including SAEs, TEAEs leading to dose reductions, TEAEs leading to discontinuation of study drug, and TEAEs leading to study withdrawal); changes in clinical laboratory parameters (hematology, serum or plasma chemistry, and urine pregnancy test), deaths, vital signs, and ECG parameters (especially QT intervals); physical examination results; and use of concomitant medications.

4.3. Measures Taken to Minimize/Avoid Bias

If a patient withdraws from the study, the data (including tested and untested samples) collected to the point of withdrawal will remain part of the study database and will not be removed.

Response criteria are based on objective measurements, as defined in RECIST v1.1, by site radiologists. All responses will be source verified; copies of tumor assessment scans will be collected and stored for future potential evaluation.

4.4. Duration of Study Treatment

Patients will continue to receive the study drug until reaching unequivocal disease progression (per RECIST v1.1), as determined by the Investigator, or experiencing unmanageable toxicity. See Section [6.4](#) for treatment beyond progression.

5. SELECTION AND WITHDRAWAL OF PATIENTS

5.1. Inclusion Criteria

Each patient must meet all of the following criteria to be enrolled in the study:

[figure not shown]
1. Is \geq 18 years of age at the time of signing informed consent
2. Has signed and dated an informed consent form prior to the start of any study-specific qualification procedures
3. Has histologically and/or cytologically confirmed diagnosis of a cancer that is a locally advanced or metastatic solid tumor
4. Has measurable tumor lesion(s) in accordance with RECIST v1.1
5. Must have received all standard therapy appropriate for their tumor type and stage of disease or, in the opinion of the Investigator, would be unlikely to tolerate or derive clinically meaningful benefit from appropriate standard-of-care therapy

6. Has resolution of any clinically relevant toxic effects of prior chemotherapy, surgery, radiotherapy, or hormonal therapy

[figure not shown]

7. Presence of WT *TP53* and *MDM2* gene amplification by tumor tissue/blood testing, defined as:
 - a. ≥ 8 copies in tumor tissue by central laboratory or
 - b. ≥ 8 copies or 4-fold increase in tumor tissue or blood by local testing

8. Has an ECOG performance status of 0 or 1
9. Has adequate bone marrow function, defined as:
 - a. Platelet count $\geq 100 \times 10^9/L$
 - b. Hemoglobin $\geq 9.0 \text{ g/dL}$
 - c. Absolute neutrophil count $\geq 1.5 \times 10^9/L$
10. Has adequate renal function, defined as creatinine clearance $\geq 30 \text{ mL/min}$, as calculated using the modified Cockcroft-Gault equation (or equivalent glomerular filtration rate calculated using the Chronic Kidney Disease Epidemiology Collaboration formula)
11. Has adequate hepatic function, defined as:

- a. Alanine aminotransferase and aspartate aminotransferase $\leq 3 \times$ the ULN if no liver metastases are present or $\leq 5 \times$ ULN if liver metastases are present
- b. Total bilirubin $\leq 1.5 \times$ ULN or $\leq 3 \times$ ULN in the presence of liver metastases. Patients with Gilbert's disease who have serum bilirubin levels of $> 3 \times$ ULN may be enrolled
12. Is willing and able to comply with the protocol requirements
13. If requiring anticoagulation medication, should be on a stable regimen, defined as being on the same dose for at least 4 weeks
14. If a WOCBP, they must have a negative serum pregnancy test at Screening and a negative urine pregnancy test on Cycle 1 Day 1 before receiving the first dose of study drug or within 72 hours of the first dose of study drug

15. If a male patient is surgically sterile and willing to use a condom or remain abstinent upon enrollment through the Treatment Period and until at least 90 days after the final dose of the study drug

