13. Is a woman who is pregnant or breastfeeding or intends to become pregnant during the study

14. Has a concomitant medical condition that would interfere with the assessment of efficacy or increase the risk of toxicity, in the opinion of the Investigator or Sponsor

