6. TREATMENT OF PATIENTS

6.1. Patient Enrollment

Selected patients may require central verification of *TP53* mutation status and /or *MDM2* amplification which can be performed under prescreening consent as outlined in the inclusion section.

Prior to any study-related assessments, all potential patients will provide written informed consent. After written informed consent has been obtained and eligibility has been confirmed, the study site will obtain the patient's identification number from the Interactive Response Technology System. Once a patient identification number has been assigned, it will be used to identify the patient throughout the study, and it cannot be reassigned to another patient.

Investigational sites will provide the Sponsor's Medical Monitor with a completed Eligibility Checklist for Sponsor review. Patients who meet the eligibility criteria may be enrolled. Patients will be considered enrolled upon their first dose of the study drug.

Patients who cannot complete the procedures within the Screening window or are not initially eligible may be rescreened. In this situation, a new patient identification number will be assigned. For rescreening within the original Screening window, certain Screening procedures may not need to be repeated. Reconsent is required for rescreening outside the original Screening window.

An Investigational Drug Accountability Log must be used for drug accountability. For additional details on investigational study drug management, please refer to the Pharmacy Manual. Patients will be provided with a patient diary to record study drug administration and compliance.

[figure not shown]

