6.5. Compliance

Investigators are required to conduct the study in compliance with the protocol. Compliance with the protocol will be closely monitored. Important aspects of compliance with this clinical study include:

- Eligibility
- Study drug administration, including dose modification
- Performance of protocol-specified assessments
- ECG monitoring
- AE reporting

Protocol deviations are defined as any departure from the protocol or associated instructions and will be monitored. Deviations from the protocol, including violations of the eligibility criteria, will be assessed as “minor” or “major”. Protocol deviations at investigational sites will be discussed with the Investigator, and additional training will be provided as needed to secure Investigator compliance.

If a deviation impacts the safety of a patient, the Investigator must contact the Sponsor immediately. The Investigator will also ensure that deviations meeting IRB/IEC and applicable regulatory authorities’ criteria are documented and communicated appropriately. All documentation and communications to the IRB/IEC and applicable regulatory authorities may be provided to the Sponsor and maintained within the Trial Master File.

Study staff will receive additional training as needed to prevent noncompliance.

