11.3. Protocol Approval and Amendment

Before the start of the study, the study protocol and/or other relevant documents will be approved by the IEC/IRB/Competent Authorities, in accordance with local legal requirements. The Sponsor or Sponsor's designee must ensure that all ethical and legal requirements have been met before the first patient provides consent to participate in the study.

This protocol is to be followed exactly. To alter the protocol, amendments must be written, receive approval from the appropriate personnel, and receive IRB/IEC/Competent Authority approval prior to implementation (if appropriate).

Administrative changes (not affecting the patient benefit/risk ratio) may be made without the need for a formal amendment. All amendments will be distributed to all protocol recipients with appropriate instructions.

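### Inclusion criterion 11b, as worded, bars Gilbert's patients without liver metastases at bilirubin above 1.5 and up to 3 × ULN, yet admits them at any value above 3 × ULN

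*Protocol*

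**What the plan says.** Criterion 11 in Protocol Section 5.1 defines adequate hepatic function. Part b gives the general limit: "Total bilirubin $\leq 1.5 \times$ ULN or $\leq 3 \times$ ULN in the presence of liver metastases". The next sentence deals with Gilbert's disease: "Patients with Gilbert's disease who have serum bilirubin levels of $> 3 \times$ ULN may be enrolled". The synopsis has the same two sentences with the same inequality and threshold: "Patients with Gilbert's disease who have serum bilirubin levels $> 3 \times$ ULN may be enrolled".

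The Gilbert's sentence does not mention liver metastases, values between 1.5 and 3 × ULN, an upper bound, or direct bilirubin.

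Three other places bear on how strictly 11b is to be taken:

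- Section 5.1, opening sentence: "Each patient must meet all of the following criteria to be enrolled in the study".
- Section 11.3: "This protocol is to be followed exactly".
- Section 6.5: "Deviations from the protocol, including violations of the eligibility criteria, will be assessed as" either minor or major.

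**The concern.** An exception for a patient group should widen the general rule. If one bilirubin value is acceptable in that group, every lower value should be acceptable too. The Gilbert's sentence in 11b does not work this way. It opens eligibility only above 3 × ULN, while the general cap without liver metastases is 1.5 × ULN, and nothing covers the band between.

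This is an operative eligibility and safety rule. A site that follows the words refuses a Gilbert's patient at 2 × ULN and may enroll the same patient at 4 × ULN. A site that treats the sentence as a waiver enrolls the patient at 2 × ULN, which the words do not allow. Above 3 × ULN, the two meanings that the sponsor could have intended lead to opposite decisions.

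**Working it through.** The plan states no figure to reproduce here. The check writes 11b as a rule and reads it off at a range of bilirubin values.

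**Inputs.** Let *b* be total bilirubin in multiples of ULN. The general cap *c* is 1.5 without liver metastases and 3 with them (Section 5.1, 11b). The Gilbert's threshold is *b* > 3 (Section 5.1 and synopsis).

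**Rules for a Gilbert's patient.**

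- Literal text: 11b is met if *b* ≤ *c* or *b* > 3.
- Waiver: 11b is met at every *b*.
- Reversed inequality: 11b is met if *b* ≤ *c* or *b* ≤ 3, which reduces to *b* ≤ 3.

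**Result at selected values** (Y = meets 11b, N = does not):

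| Rule | Liver metastases | 1.5 | 1.6 | 2 | 3 | 3.1 | 5 | 10 |
|---|---|---|---|---|---|---|---|---|
| Literal | no | Y | N | N | N | Y | Y | Y |
| Literal | yes | Y | Y | Y | Y | Y | Y | Y |
| Waiver | either | Y | Y | Y | Y | Y | Y | Y |
| Reversed | either | Y | Y | Y | Y | N | N | N |

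**What follows.**

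1. Without liver metastases, the literal rule accepts *b* ≤ 1.5, rejects 1.5 < *b* ≤ 3, and accepts *b* > 3 without limit. It is the only rule in the table under which eligibility improves as bilirubin rises.
2. With liver metastases, the literal rule is *b* ≤ 3 or *b* > 3, so 11b sets no bilirubin limit. It coincides with the waiver and has no gap.
3. Patients without Gilbert's disease are unaffected: their cut-offs are 1.5 and 3 × ULN, and neither rule has a gap.
4. Compared with the literal text, the waiver adds 1.5 < *b* ≤ 3 without liver metastases and removes nothing. The reversed inequality adds the same band and removes everything above 3, with or without liver metastases.
5. Both candidate meanings therefore admit the band that the literal text rejects. The wording needs correcting whichever was meant.

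**Which meaning is more likely.** The sentence comes directly after the 3 × ULN cap and is permissive, which fits a waiver. Under the reversed inequality it would also do no work for patients with liver metastases, whose general cap is already 3 × ULN. Both points favor the waiver, but neither proves it.

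**The case against.** The strongest reply is that no clinician would apply the literal rule. Accepting 4 × ULN and refusing 2 × ULN in the same condition makes no sense, so a reader would take the sentence as a waiver and move on. That is the better reading of intent, and much of this reply stands. It does not make the written criterion correct. The sentence names only patients above 3 × ULN, and Sections 5.1 and 11.3 ask for the text to be followed.

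The second reply is that other safeguards exist:

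- The transaminase caps in 11a still apply.
- Exclusion 14 allows refusal of a patient who "Has a concomitant medical condition that would interfere with the assessment of efficacy or increase the risk of toxicity".
- Under Section 6.1, sites supply the Medical Monitor "with a completed Eligibility Checklist for Sponsor review".
- Section 8.9 requires laboratory results to be evaluated before dosing and gives Grade ≥ 2 serum bilirubin as an example of a reportable result.
- SAP Section 6.5.6 lists potential Hy's Law cases.

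Patients with high bilirubin are therefore not unmonitored. None of these safeguards admits the skipped band or sets a bilirubin ceiling for entry.

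The third reply concerns redaction. Parts of the eligibility sections are blacked out, and the text on dose modifications is absent. In both places 11b runs into criterion 12 without a visible gap, so a hidden note at that spot is unlikely. A clarification elsewhere cannot be excluded, and the point is limited to the visible text.

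A reader might go further and infer that the inequality was simply typed the wrong way round and that 3 × ULN should be imposed as a ceiling. The documents do not support this. Enrollment above 3 × ULN is the one thing that both versions of the clause expressly allow, and nothing visible withdraws it. A reader might also infer that sites are confused or that eligibility violations will occur. No passage shows this. If the sponsor intends and applies a waiver, an enrollment at 2 × ULN might not be classed as a violation at all. If it were classed as a significant deviation, Section 5.3 lets the patient continue when the Investigator and Medical Monitor agree and the IRB or IEC approves.

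**Conclusion.** Criterion 11b is wrong as written for Gilbert's patients without liver metastases. It rejects total bilirubin above 1.5 and up to 3 × ULN and accepts any value above 3 × ULN. This conclusion needs only the words of the criterion, which are the same in Section 5.1 and the synopsis, so an error in reading the PDF is unlikely. A waiver is the more probable intent, but the visible text does not settle it.

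Severity is minor. The documents give neither the frequency of Gilbert's disease nor a distribution of bilirubin, so no count of affected patients can be derived. Few of the approximately 65 are likely to be concerned. The gap itself touches only those with Gilbert's disease, no liver metastases and bilirubin within the skipped band. The lack of a ceiling applies to all Gilbert's patients, but whether one is needed is a clinical judgment, and the documents show no harm from its absence. Sample size and the ORR analysis are not affected.

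**What to change.** Ask the sponsor's medical lead which rule was meant. Then replace the Gilbert's sentence in Section 5.1 and in the synopsis, and carry the change into the Eligibility Checklist. Whatever wording is chosen should admit the band above 1.5 and up to 3 × ULN and should never make a higher value eligible where a lower one is not.

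- Smallest change consistent with the present text: *In patients with Gilbert's disease the total bilirubin limits above do not apply, including values > 3 × ULN.* The medical lead adds a ceiling if one is wanted.
- If the sponsor confirms that the inequality was reversed: *Patients with Gilbert's disease may be enrolled with total bilirubin ≤ 3 × ULN.* This withdraws the present allowance above 3 × ULN, so it should be used only with that confirmation.

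The cost is one clause in two places plus the checklist. Neither wording needs a new test, because total bilirubin is already in Table 6 of Section 8.9. A ceiling expressed in direct bilirubin would need an added Screening test for Gilbert's patients, since that table does not list it.
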